8.3.5 Medical history

Medical history will be summarized for the ITT set and the Add-on Treatment set.

Medical history will be coded using the Medical Dictionary for Regulatory Activities (MedDRA®) coding system version 23.1 or later version. Medical history will be summarized by System SOC and PT of the MedDRA® dictionary by treatment group and overall.

A patient data listing will be provided.

8.4 Efficacy analyses

8.4.1 Primary analysis

The primary analyses will be performed using the CCI set.

Definition of primary endpoint

Overall Response Rate (ORR) defined as the proportion of patients in whom a CR or PR is observed as best overall response by blinded independent central review (BICR).

The BICR will provide a response for each patient assessment using the RECIST[©] 1.1 guidelines.

Main analytical approach

The primary statistical objective is to demonstrate that the ORR of BNT111+cemiplimab is greater than CCI using an overall significance level of CCI using an overall significance level of

[figure not shown]
The following null and alternative hypothesis are defined:

[figure not shown]
Statistical Analysis Plan (SAP) BNT111-01

Page 37 of 78 Version: Final v7.0 Date: 05Mar2024

The best overall response for a patient is defined as the best response across all responses prior to the start of new anti-cancer therapy for that patient. It is noted that a tumor response of SD can be confirmed from 36 days after first dose of study drug as the tumor assessment at week 6 (day 42) can be performed in a +/- 1 week window.

[figure not shown]
Statistical analysis

Additionally, a swimmer plot for duration on treatment and overall response assessments based on RECIST for BICR assessment will be presented based on set, add-on treatment set and combination of both (show both periods, including only for patients entering add-on treatment set). For IA1 the plot was generated for patients with BOR of CR/PR/SD and for IA2 the plot will be generated for patients with BOR of CR/PR/SD/PD/NE (for BICR data, the category Non-CR/Non-PD will be added). Tumor response and overall response will be listed.

Sensitivity analysis

Additionally, sensitivity analysis based on confirmed CR/PR (RECIST 1.1) for BICR assessment for the CCI set will be performed.

Page 38 of 78 Version: Final v7.0 Date: 05Mar2024

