- q Tumor response will be measured by RECIST 1.1 / iRECIST. Patients will undergo tumor assessments at screening, every 6±1 wks for the 3 mon after trial treatment start, every 9±1 wks for the next 9 mon, and every 12±2 wks thereafter, regardless of dose delays, until (confirmed) disease progression (even if the patients discontinue trial treatment for other reasons) or until the start of next-line anti-cancer therapy (whichever occurs first). An extra scan should be scheduled if clinically indicated. Patients in Arms 2 and 3 who experience (confirmed) disease progression under single-agent treatment may be offered addition of the respective other compound to the ongoing treatment. In such cases, tumor assessments are to continue, and additional images should be collected in accordance with the imaging schedule and modalities outlined in Section 1.3.2.
- r All measurable and evaluable lesions should be assessed at screening and target as well as non-target lesions identified and documented following RECIST 1.1 criteria. Tumor assessments, including brain imaging, performed as standard of care prior to obtaining informed consent and within 28 d prior to randomization do not have to be repeated at screening. Radiological progression to be confirmed by two scans, 4 to 12 wks apart. If progression is accompanied by new symptoms or deterioration of PS not attributed to toxicity, one scan is sufficient.
- s Any brain lesions present at screening must be stable as per eligibility criteria and should be followed and assessed at all subsequent tumor assessment visits. Brain imaging performed as standard of care prior to obtaining informed consent and within 28 d prior to randomization do not have to be repeated at screening. If no brain lesions are present at screening, brain imaging does not need to be repeated, only if clinically indicated as per investigator judgment. Brain imaging should be done by MRI, only in the case of a contra-indication for MRI, a contrast-enhanced CT brain scan will be acceptable.

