9.4.3 Secondary endpoints

The secondary analyses will be performed using the CCI set.

The secondary endpoints related to tumor assessments (e.g., DCR, DOR, PFS) are based on independent read using RECIST 1.1 criteria. The endpoints based on iRECIST criteria will be evaluated as exploratory analysis. The endpoints based on investigator's criteria will be evaluated as exploratory analysis.

Disease control rate

DCR is defined as the proportion of patients in whom a CR or PR or SD (SD assessed at least 6 wks [+/- 1 wk] after first dose) is observed as best overall response. Patients not meeting the criteria for CR or PR or SD, including those without any post-randomization tumor assessments, will be considered as non-responders.

DCR will be summarized with absolute and relative frequencies along with two-sided Clopper-Pearson 95% confidence intervals by treatment group.

Time to response

TTR is defined as the time from randomization to first objective response (CR or PR). Only patients in whom a CR or PR is observed will be analyzed for TTR.

TTR will be analyzed using summary statistics by treatment group.

Duration of response

DOR is defined as the time from first objective response (CR or PR) to first occurrence of objective tumor progression (PD), or death from any cause, whichever occurs first. Only patients in whom a CR or PR is observed will be analyzed for DOR.

DOR will be analyzed using Kaplan-Meier methodology by treatment group. Patients alive and without disease progression at data cut-off date or patients lost to follow-up will be censored at the day of their last tumor assessment. Additional censoring rules will be defined in the SAP.

Page 94 of 133 Version: 7.0 Date: 09 FEB 2023

Progression-free survival

PFS is defined as the time from randomization to first objective tumor progression (PD according to RECIST 1.1), or death from any cause, whichever occurs first.

PFS will be analyzed using Kaplan-Meier methodology by treatment group/cohort. Patients alive and without disease progression or patients lost to follow-up at data cut-off date will be censored at the day of their last tumor assessment. Additional censoring rules will be defined in the SAP.

Overall survival

OS is defined as the time from randomization to death from any cause.

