An analysis update will be performed when the last patient discontinued from the trial and once all patients have been randomized and have been followed-up for at least 24 months. An analysis update may be subsequently performed.

Statistical Analysis Plan (SAP) BNT111-01

Page 30 of 78 Version: Final v7.0 Date: 05Mar2024

Data up to and including the clinical cut-off date will be taken into account for the statistical analysis.

All analyses will be conducted using SAS® version 9.4 or higher.

Baseline is defined as last non-missing value prior to the first dose of trial treatment at C1D1. Assessments performed at C1D1 will be considered for baseline value, unless there is evidence the assessment was performed after trial treatment had been administered. For the add-on treatment if the baseline visit and AOC1D1 are on the same day, the assessment only needs to be taken once. In this case the AOC1D1 would be considered as the baseline value, unless there was evidence that the assessment was done after treatment had been administered.

To identify the baseline value, generally, if there are multiple assessments available for a particular day, the assessment that is closest to the day (and time if collected) of the first dose of the trial treatment (i.e., BNT111 or cemiplimab) will be used as the baseline value in the summary/analyses.

Multiple values at post-baseline visits: if there are multiple post-baseline assessments available within a visit/day, the first value and corresponding date/time will be considered.

Change from baseline will be calculated as follows:

Change from baseline = post-baseline assessment value – baseline assessment value.

If either the baseline or post-baseline assessment value is missing, the change from baseline is set to missing as well.

Duration (Other than "trial treatment duration" defined in Section 8.5.1) will be calculated as follows:

Duration = last observation date - first observation date + 1

For conversion of days to months or years the following rules will be applied:

- 1 month = 30.4375 days
- 1 year = 365.25 days

Trial Day and Treatment Day are defined as follows:

- Trial day:
 - If assessment date < randomization date then trial day = assessment date randomization date
 - If assessment date >= randomization date then trial day = assessment date randomization date + 1
- Treatment Day = treatment date date of first dose +1

That is, trial day 1 indicates the date of treatment initiation.

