8.4.2.2 Disease Control Rate (DCR) using BICR and RECIST 1.1

DCR is defined as the proportion of patients in whom a CR or PR or SD (for BICR data, the Non-CR/Non-PD response will be included in the DCR, similarly to SD response) (SD assessed at least 6 weeks [+/- 1 wk] after first dose) is observed as best overall response. Patients not meeting the criteria for CR or PR or SD (for BICR data, the Non-CR/Non-PD response will be included), including those without any post-randomization tumor assessments, will be considered as non-responders. Only patients with adequate (i.e. available) baseline and post-baseline assessments, in whom a CR, PR or SD is observed will be analyzed.

DCR will be summarized as a binary endpoint along with ORR (Section 8.1).

If the sensitivity analysis of ORR for the CCI and CCI and is done then a summary of DCR will also be included.

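### SAP 8.4.1 mixes two day-counting conventions for the earliest acceptable SD: its 36 days after first dose should read 35 days, which is Day 36 when first dose is Day 1

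*SAP*

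**What the plan says.** SAP 8.4.1 notes that "a tumor response of SD can be confirmed from 36 days after first dose of study drug" and gives as its reason "as the tumor assessment at week 6 (day 42) can be performed in a +/- 1 week window". This is the only place in either document where the minimum time for SD is given as a number of days.

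The endpoint definitions give weeks only. SAP 8.4.2.2 counts SD in DCR when it is "SD assessed at least 6 weeks [+/- 1 wk] after first dose". Protocol 9.4.3 has the same rule, and SAP 8.4.3.2 repeats it for duration of disease control (DDC). The scan schedule in Protocol 1.3.1 (footnote q) is "every 6±1 wks for the 3 mon after trial treatment start".

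On day counting, SAP 8.1 adds one day: "Duration = last observation date - first observation date + 1", and "That is, trial day 1 indicates the date of treatment initiation". SAP Appendix 7 counts scan days from first dose and sets the week-6 target at day 43. It applies to the depth-of-response analysis.

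SAP 8.1 also says that best overall response is derived by program under a separate guideline. That guideline is not among the documents.

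**The concern.** The sentence in 8.4.1 does not agree with its own derivation. Day 42 less seven days is 35, yet the printed threshold is 36 days after first dose. Taken at its word, the sentence starts one day later than the DCR and DDC definitions allow.

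DCR is built on best overall response, and this sentence sits in the paragraph that defines best overall response. A programmer who wants a number for the SD minimum will find only this one. DCR by BICR is a secondary endpoint and a subgroup endpoint (SAP 7.3). The same SD rule carries into investigator-assessed DCR (8.4.2.6), the iRECIST analyses (8.4.3.1) and DDC (8.4.3.2 and 8.4.3.3). A one-day shift would therefore run through several tables.

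SAP 10.8 makes the early edge of the window slightly more relevant. It dates an SD assessment at the earlier of the target and non-target lesion dates, so an assessment spread over several days is dated towards that edge.

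**Working it through.** **Inputs.** Week-6 scan with a window of 7 days either side (Protocol 1.3.1, SAP 8.4.1); week 6 written as day 42 (SAP 8.4.1); week-6 target day 43 (SAP Appendix 7); first day counted as Day 1 (SAP 8.1); 90 patients planned in Arm 1 (SAP Table 3.2).

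**Reproducing the plan's figure.** With first dose as Day 1, week 6 is 6 × 7 + 1 = Day 43, and 43 − 7 = Day 36. This gives 36, as a day number.

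**The sentence's own figures.** 42 − 7 = 35. If day 42 means 42 elapsed days, the threshold is 35 days after first dose. If it means Day 42 with first dose as Day 1, then 42 − 7 = Day 35, which is 34 elapsed days. Neither reading gives 36, so the day 42 and the 36 cannot belong to the same convention.

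**The DCR definition.** 6 × 7 − 7 = 35 elapsed days, which is 35 + 1 = Day 36.

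**Is an SD scan at 35 elapsed days accepted?**

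| Reading | Condition | Accepted? |
|---|---|---|
| 8.4.1 as elapsed days | elapsed ≥ 36 | No |
| 8.4.1 as Day 36, first dose = Day 1 | elapsed ≥ 35 | Yes |
| DCR definition (SAP 8.4.2.2, Protocol 9.4.3) | elapsed ≥ 35 | Yes |

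**Size under the elapsed-day reading.** The window runs from 35 to 49 days, which is 15 days, and one of them is lost. The documents give neither the spread of scan days nor the share of patients whose only non-PD result is SD at that scan, so both are assumed here.

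- Scan days uniform over the window: 1/15 = 6.7% of first scans fall on day 35. With 25% of these patients having SD only at that scan: 6.7% × 25% = 1.7% of patients, and 90 × 0.25 / 15 = 1.5 patients.
- Scan days normal around day 42 with a standard deviation of 3 days: the probability of day 35 is about 0.9%. Then 0.9% × 25% = 0.2% of patients, and 90 × 0.009 × 0.25 = 0.2 patients.
- Varying the SD-only share from 10% to 30% with uniform scan days: 90/15 × 0.10 = 0.6 to 90/15 × 0.30 = 1.8 patients, or 0.7 to 2.0 percentage points of DCR.

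Under the Day 36 reading the loss is zero.

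**The case against.** The best defence is that 36 is the right answer under the SAP's own conventions. Section 8.1 counts the first day as Day 1, Appendix 7 puts week 6 at day 43, and 43 − 7 = 36 is exactly the first permitted day. The version history (Final 5.0, Section 8.4.1) logs the sentence as a clarification. SAP Appendix 1 lists no change to the SD minimum among the departures from the protocol. The sentence exists to accommodate the scan window, so a reading that cuts a day off that window works against its purpose. The DCR and DDC sections contain no 36-day cut-off, and the operative algorithm is in a guideline that cannot be seen.

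Most of this stands, and it rules out a stronger reading that a reader might infer: that an SD scan on the first permitted day is not counted in DCR. The documents do not say so. That would follow only if the threshold were programmed as elapsed days.

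The defence does not rescue the sentence itself, which says days after first dose rather than Day 36 and uses day 42 rather than Day 43. Section 8.1 does not fully settle the matter either. It defines trial day from randomization and treatment day from first dose, then summarizes by saying that trial day 1 is treatment initiation. SOA1 places randomization at C1D1, so the two normally coincide, but the text does not tell a programmer which count the 36 refers to.

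**Conclusion.** The sentence is wrong as written: its threshold and its derivation use different day conventions, and read literally it is one day stricter than the DCR definition in both documents. Whether any patient is affected is not known, because that depends on a programming guideline outside the documents. Confidence in a practical effect is therefore no more than moderate.

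If the rule is applied as elapsed days, the loss is confined to patients whose qualifying SD scan falls exactly 35 days after first dose and who have no later SD, CR or PR. That is about 0.2 to 1.5 of 90 patients in Arm 1, resting on the assumed scan-day distributions and the assumed 25% share. If it is applied as Day 36, nobody is lost. ORR, the primary endpoint, does not depend on SD and is unaffected. DCR is reported descriptively with a confidence interval and no test, so no formal decision turns on it. This is a minor correction that is worth making because it is almost free.

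**What to change.** In SAP 8.4.1, replace the threshold with: *from 35 days after first dose (Day 36, with first dose = Day 1 and week 6 = Day 43)*, and drop the reference to day 42. State the same convention in the best-overall-response programming guideline and apply it in DCR (8.4.2.2) and DDC (8.4.3.2, 8.4.3.3). Check that the existing code accepts an SD scan dated 35 days after first dose.

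The cost is one SAP sentence and one check of the code. The protocol definition does not change, and neither do the sample size, the ORR analysis or the scan schedule.

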8.4.2 Secondary analyses

The secondary analyses will be performed for the BNT111 + cemiplimab, BNT111 (mono) and cemiplimab (mono) treatment groups, apart from overall survival which is secondary analysis for the BNT111 + cemiplimab treatment group only. All analyses will be done using the CCI set, unless specified otherwise.

8.4.2.1 Key Secondary Analysis

As described in Section 4 the primary endpoint (ORR) will be analyzed descriptively for the calibrator groups BNT111 (mono) and cemiplimab (mono), in a non-confirmatory sense in order to obtain an estimate for the single agent anti-cancer activity. Summaries as for the primary analysis will be presented.

8.4.2.2 Disease Control Rate (DCR) using BICR and RECIST 1.1

DCR is defined as the proportion of patients in whom a CR or PR or SD (for BICR data, the Non-CR/Non-PD response will be included in the DCR, similarly to SD response) (SD assessed at least 6 weeks [+/- 1 wk] after first dose) is observed as best overall response. Patients not meeting the criteria for CR or PR or SD (for BICR data, the Non-CR/Non-PD response will be included), including those without any post-randomization tumor assessments, will be considered as non-responders. Only patients with adequate (i.e. available) baseline and post-baseline assessments, in whom a CR, PR or SD is observed will be analyzed.

DCR will be summarized as a binary endpoint along with ORR (Section 8.1).

If the sensitivity analysis of ORR for the CCI and CCI and is done then a summary of DCR will also be included.

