Treatment and trial duration	Patient level: Patients will receive treatment BNT111 + cemiplimab or BNT111 or cemiplimab, single agents up to 24 months and will continue until unacceptable toxicity, withdrawal of consent, discontinuation due to investigator's decision or (confirmed) disease progression. The duration of therapy for patients entering into add-on therapy is a total of 24 months for both the monotherapy and add-on therapy part. Trial level: Approximately 18 months of recruitment followed by approximately up to 48 months
	of OS follow-up from the randomization of last patient.
Planned number of patients	180 patients will be randomized overall (90 patients to Arm 1 (BNT111 + cemiplimab) and 45 patients each to calibrator Arms 2 (BNT111 mono), and 3 (cemiplimab mono).
Randomization and	Automated centralized randomization.
blinding	Stratification factors: metastatic status: M0, M1a, M1b versus M1c, M1d and by number of prior lines of systemic treatment (1 vs 2 to 5) Treatment Allocation Ratio: 2:1:1 Blinding: Open-label
Tumor assessment schedule:	Tumor response assessments will be performed at screening, every 6 (±1) weeks for the first 3 months after randomization, then every 9 (±1) weeks for the next 9 months and every 12 (±2) weeks thereafter. Until (confirmed) disease progression, death, withdrawal of consent, or until the start of next-line anti-cancer therapy, whichever occurs earlier. Tumor response will be assessed by investigator as well as by blinded independent central review (BICR) of radiographic images and will be measured using RECIST 1.1 and iRECIST.
	The same schedule will be followed if a patient receives Add-on treatment.
Other features	Per the IDMC charter, regular meetings by an IDMC will be scheduled to review and evaluate safety data. Details on the meeting frequency are described in Section 5.1. of this SAP. Review of Interim analysis will occur per Section 5.2 of this SAP.

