8 STATISTICAL ANALYSES

8.1 General considerations

In general, the statistical analysis of efficacy will be performed by treatment group. Exploratory analysis will be performed for patients in the calibrator arms who went on to receive add-on treatment.

No formal statistical comparisons between treatment groups will be performed.

Continuous variables will be summarized by treatment group and total (as specified) using the following descriptive statistics: number of patients with non-missing data (n), mean, standard deviation (SD), median, minimum (min) and maximum (max).

Categorical variables will be summarized by treatment group and total (as specified), presenting absolute and relative frequencies (n and %) of patients in each category and the number of patients with missing data (missing' category will be presented if there is one or more missing value). The "(N=xx)" in the tables denotes the number of patients in the

Statistical Analysis Plan (SAP) BNT111-01

Page 28 of 78 Version: Final v7.0 Date: 05Mar2024

analysis set within each treatment group. For event-driven occurrence data (e.g., adverse event, concomitant medication, etc.) the percentages will be based on the number of patients in the analysis set (N). For reported visit data (e.g., gender, ECOG, etc.) the percentages will be based on the number of patients with non-missing values (n).

The rates of binary endpoints will be summarized by treatment group with absolute and relative frequencies (n and %) along with two-sided 95%-confidence intervals (CI) using an exact method. Exact confidence intervals for binomial proportions will be derived using the Clopper-Pearson method (Clopper, CJ and Pearson, ES⁵).

Time-to-event-endpoints will be analyzed using Kaplan-Meier methodology by treatment group and censored in accordance with the FDA Guidance: "Clinical Trial Endpoints for the Approval of Non-Cell Lung Cancer Drugs and Biologics² (Table 5.1). The main analysis will be done for each treatment group separately. Comparison of the treatment groups may be done as an exploratory analysis, with stratified and non-stratified analysis considered.

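### SAP 8.4.2.2 limits the DCR analysis to patients who already have disease control, so the rate is 100% as written and contradicts the non-responder rule in the preceding sentence

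*SAP*

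**What the plan says.** SAP 8.4.2.2 opens with a proportion: "DCR is defined as the proportion of patients in whom a CR or PR or SD" is the best overall response. SD must be assessed at least 6 weeks (±1 week) after first dose, and for BICR data Non-CR/Non-PD counts in the same way as SD. Patients who do not meet the criteria, "including those without any post-randomization tumor assessments, will be considered as non-responders".

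The next sentence reads: "Only patients with adequate (i.e. available) baseline and post-baseline assessments, in whom a CR, PR or SD is observed will be analyzed". The section then has DCR summarized as a binary endpoint beside ORR, under SAP 8.1, where "Exact confidence intervals for binomial proportions will be derived using the Clopper-Pearson method".

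Protocol 9.4.3 has the non-responder rule alone: "Patients not meeting the criteria for CR or PR or SD, including those without any post-randomization tumor assessments, will be considered as non-responders". Protocol 9.4.2 treats unscanned patients as non-responders for ORR as well. SAP 10.1 (Appendix 1), which lists changes to the protocol-planned analyses, mentions the addition of Non-CR/Non-PD to DCR but no restriction of the DCR population.

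**The concern.** A response-type rate needs its failures in the denominator. The restriction removes exactly the patients whom the previous sentence keeps as failures, and it selects on the outcome being estimated. A near-identical sentence in SAP 8.4.2.3 is right for duration of response, which exists only in responders. It does not suit a rate.

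DCR is a named secondary endpoint in all three arms. Section 8.4.2.2 is called again for the investigator reads (8.4.2.6), iRECIST (8.4.3.1), the add-on set (8.4.3.5), the subgroups (7.3) and the second interim analysis (5.2). DCR is tabulated beside ORR, so a reader could see two rates for the same arm on different denominators without being told.

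**Working it through.** **Inputs.** The planned arm sizes are in SAP Table 3.2: 180 patients at 2:1:1, so 180 × 2/4 = 90 in Arm 1 and 180 × 1/4 = 45 in each calibrator arm. The documents give no expected DCR and no expected number of unscanned patients, so there is no plan figure to reproduce. The rates (30%, 50%, 70%) and the unscanned numbers below are assumptions, shown over a range.

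Let *N* be the patients in the arm, *x* those with disease control and *m* those with no post-baseline scan. Intervals are exact 95% Clopper-Pearson.

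**1. Non-responder rule (protocol, and the earlier SAP sentence).** DCR = *x*/*N*.

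**2. Restriction read literally.** Only the *x* patients with an observed CR, PR or SD are analyzed, so DCR = *x*/*x*.

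| Arm size | Rule 1 (95% CI) | Rule 2 (95% lower limit) |
|---|---|---|
| 90 | 27/90 = 30.0% (20.8 to 40.6) | 27/27 = 100% (87.2) |
| 90 | 45/90 = 50.0% (39.3 to 60.7) | 45/45 = 100% (92.1) |
| 90 | 63/90 = 70.0% (59.4 to 79.2) | 63/63 = 100% (94.3) |
| 45 | 14/45 = 31.1% (18.2 to 46.6) | 14/14 = 100% (76.8) |
| 45 | 22/45 = 48.9% (33.7 to 64.2) | 22/22 = 100% (84.6) |
| 45 | 31/45 = 68.9% (53.4 to 81.8) | 31/31 = 100% (88.8) |

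There is one narrow exception. SAP 8.4.1 says that "a tumor response of SD can be confirmed from 36 days after first dose of study drug". A patient with SD seen only before then could be taken as having an observed SD, and so enter the denominator without entering the numerator. With 45 controlled patients, one such case gives 45/46 = 97.8% and five give 45/50 = 90.0%.

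**3. Restriction read mildly (drop only unscanned patients).** DCR = *x*/(*N* − *m*), which is rule 1 multiplied by 1/(1 − *m*/*N*). With *x* = 45 and *N* = 90:

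- *m* = 5: 45/85 = 52.9%
- *m* = 9: 45/81 = 55.6%
- *m* = 4 to 14 (about 5% to 15% of 90): 45/86 = 52.3% to 45/76 = 59.2%

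The factor depends only on the unscanned fraction, so the inflation is greatest in the arm with most early dropout. Under this reading a patient whose scan shows PD stays in as a failure. The patients lost are those who die, progress clinically or withdraw before any scan.

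**4. Does the SAP settle it elsewhere?** It does not. SAP 8.1 gives two percentage bases, the analysis-set *N* for event-driven data and the non-missing *n* for visit data, and does not say which applies to best overall response. The restriction also names CR, PR and SD but omits Non-CR/Non-PD, which the same section counts as disease control for BICR. Whether those patients are analyzed is therefore unclear as well.

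**The case against.** The best defence is that nobody would program the literal reading. The section calls DCR a proportion, names non-responders and asks for a binary summary with an exact interval. A table showing 100% in every arm would be noticed at once. The SAP version history logs the v6.0 edits to 8.4.2.2 and 8.4.2.3 in the same words, as clarifications, which suggests that wording meant for duration of response was carried across. That origin is an inference, but a reasonable one, and programmers would probably follow the non-responder rule.

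The milder figures also depend on an analysis set whose name is blacked out. If it were the mITT set, which already requires a baseline and a post-randomization assessment, the mild reading would remove almost nobody. DCR also carries no hypothesis, alpha or decision rule.

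These points limit the consequence but do not remove the contradiction. In the mITT set the literal sentence would still exclude every patient whose best response is PD, because it conditions on outcome in any set. The clause about patients never scanned would have no work to do in that set, which suggests a set that includes them. The mild reading is the realistic hazard because it yields a plausible number that would not stand out.

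**Conclusion.** The concern holds. Two adjacent sentences define incompatible denominators, and the second departs from the protocol without being listed as a change. On its natural reading DCR is 100% in every arm; the only exception is an SD seen before day 36 being counted as observed. The more likely practical error is upward bias: about 3 to 6 percentage points at an assumed 50% rate with 5 to 9 of 90 patients unscanned, and up to about 9 points if 15% are unscanned. Those sizes rest on an assumed rate, assumed dropout and an analysis set that includes unscanned patients. The primary ORR test and its type I error are not affected. What is affected is a descriptive secondary endpoint wherever section 8.4.2.2 is reused.

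**What to change.** Delete the restriction sentence from SAP 8.4.2.2, leaving its counterpart in 8.4.2.3 for duration of response. In its place, state the following:

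- The DCR denominator is every patient in the analysis set used for ORR in the same table.
- Patients without CR, PR, a qualifying SD or (for BICR) Non-CR/Non-PD, and patients without a post-baseline scan, count as not having disease control.
- The same rule applies wherever 8.4.2.2 is reused.

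If the sponsor wants a rate among scanned patients only, it should be a labelled supplementary summary and be listed in SAP 10.1.

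The cost is one sentence removed and a short statement added, with no new data. Any DCR output already programmed from this section should be checked for the denominator used. If unscanned patients were dropped, the reported DCR will fall slightly.
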